### **Study Background and Rationale**

The incidence of cesarean delivery in the United States has increased significantly over the past few decades, with an incidence of 33% in New York State alone per the CDC's National Center for Health Statistics in 2019 [1]. Despite the abundance of existing literature on the benefits of subcuticular skin closure over staples, there is limited data on other methods of cesarean skin closure, such as tissue adhesives and skin glue. This method has recently been examined in the non-obstetric literature due to possible advantages of decreased operative time, the ability to provide a waterproof barrier, and antimicrobial properties of tissue adhesives [2-3].

Dermabond Prineo is a tissue adhesive that has been used for skin closure in the gynecologic, plastics, and cardiothoracic surgery literature, but has not yet been utilized for obstetric surgery. Known advantages of Dermabond Prineo in comparison to subcuticular suture include greater skin holding strength, which has been shown in non-obstetric studies to be 40% stronger compared to 4-0 sutures and 33% stronger than staples. Dermabond Prineo has been shown to have better cosmetic results according to patient and observer scar assessment scales, and shorter closure time by up to 84% as it dries in 60 seconds. This method eliminates the need for postsurgical dressings, and has a waterproof antimicrobial barrier that has been shown in invitro studies to be 99% effective for 72 hours against SSI organisms. In comparison, traditional dissolvable suture can be a site of bacterial colonization for infection, and can create inconsistent suture tension distribution across the incision which can compromise both the integrity and cosmesis of the closure. Cesarean section incisions closed with suture are typically covered with a sterile dressing; however, these dressings do not have antimicrobial properties, and may increase the risk for infection if removed too early or too late as patients are unable to shower with the bandage on. In comparison, patients with Dermabond Prineo can shower immediately after surgery, as the mesh layer falls off on its own or can be removed in 7-14 days [4-6].

We propose a quality assessment initiative, through a randomized controlled trial designed to investigate the role of tissue adhesives such as Dermabond Prineo on outcomes such as cesarean wound cosmesis, operative times, and SSI.

### **Objective**

The primary outcome of the current study is to assess patient satisfaction with cesarean scar cosmesis when comparing standard subcuticular suture closure to the Dermabond Prineo tissue adhesive system. This outcome will be assessed with the validated Patient Scar Assessment Scale

(PSAS) [7]. This questionnaire has previously been used in the skin staples versus suture obstetric literature [8].

### **Primary Research Question / Hypothesis**

Does Dermabond Prineo provide improved patient scar satisfaction when compared to standard subcuticular suture?

### **Secondary Research Questions**

1. Does Dermabond Prineo decrease the rate of wound complications after cesarean section when compared to standard subcuticular suture?
2. Does Dermabond Prineo decrease overall skin closure time and operative time at the time of cesarean section when compared to standard subcuticular suture?
3. Is Dermabond Prineo associated with decreased postoperative pain scores after cesarean section when compared to standard subcuticular suture?

### **Exposure**

Dermabond Prineo  
Standard subcuticular suture

### **Arms**

Group 1: Dermabond Prineo for skin closure at time of cesarean section  
Group 2: Standard subcuticular suture for skin closure at time of cesarean section

### **Study Design**

This will be a prospective randomized, open label trial as both surgeons and patients will know what type of closure technique is utilized. Two study groups will be defined as described above. In group 1, Dermabond Prineo will be utilized in place of standard subcuticular closure at the time of cesarean skin closure. In group 2, standard subcuticular closure will be utilized at the time of cesarean skin closure. All patients will be randomized immediately preoperatively as part of the multidisciplinary preoperative briefing process. See procedure below for further details.

### **Inclusion Criteria**

- Women age 18 years or older
- Admitted to CHONY Labor and Delivery unit

- All women scheduled for primary or repeat cesarean deliveries
- All women undergoing intrapartum or antepartum cesarean delivery
- Pfannenstiel skin incision
- Birth of a live infant at time of cesarean delivery

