#### Sample Size Calculation

The primary outcome of our study will be the Patient Scar Assessment Scale (PSAS), which has a range of potential scores from 6-60). The following assumptions were used for the parameters in our sample size calculation:

Power: 80%

Alpha level: 0.05 (two-sided)

Mean  $\pm$  SD for suture group:  $20 \pm 6$

Effect size: 20% reduction (relative to the control group)

Loss to follow up: 20%

Allocation Ratio: 1:1

The distributions of both groups are assumed to be normal.

The standard deviation for both groups is assumed to be the same.

The results were calculated in Stata/BE 17.0

With these assumptions, our total sample size is calculated to be 188 total patients, with 94 patients in each arm.

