## Procedures

Permission from primary teams will be sought on Columbia University Medical Center: New York Presbyterian – Children’s Hospital of New York (CHONY) labor and delivery and informed consent obtained from women willing to participate in the study. Women scheduled for cesarean delivery will be contacted by the research team via 1 of 3 options: 1) via telephone to obtain telephone consent in the week prior to their scheduled procedure; 2) in person at the last outpatient visit prior to their scheduled c-section; 3) in person at the time of admission to labor and delivery for their scheduled procedure if they cannot be contacted beforehand. Women admitted to the antepartum service or labor and delivery for induction of labor or spontaneous labor who then undergo intrapartum cesarean delivery will be consented at the time the decision is made to proceed with cesarean.

Once consent is obtained, randomization will be performed using a computer-generated algorithm. Consenting women will be randomly assigned in a 1:1 ratio to each group by trained research personnel. Women meeting inclusion criteria will be randomized to two groups: 1) experimental arm: Dermabond Prineo skin closure at the time of cesarean section; or 2) control arm: standard subcuticular skin closure at the time of cesarean section. Following randomization, the assigned intervention will be announced to the surgical team at the time of the surgical time-out in the operating room, dictating either standard subcuticular skin closure or closure with Dermabond Prineo, both of which will be available in the Labor and Delivery operating rooms. Those who receive standard subcuticular skin closure will have their incision covered by a standard pressure dressing, as per routine protocol. Those who receive Dermabond Prineo will forego the application of an additional pressure dressing, as one of the benefits of the Dermabond Prineo closure is that an overlying dressing is no longer necessary. Thus, this is an open label trial as both the surgical team and the patient will be able to visualize what type of closure technique was utilized.

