In terms of immediate postoperative wound assessment on postoperative day 3, a member of the surgical team will perform a standard postoperative wound assessment prior to hospital discharge to assess for evidence of the wound complications, including the presence or absence of superficial SSI, deep SSI, endometritis, and/or wound disruption. Postoperative pain scores are also documented for all patients by postpartum nursing staff as part of routine postoperative care, and will be assessed for patients in both groups.

Long term postoperative follow up will then be assessed by the research team at 4-6 week postoperative follow up visits. Patients will be consented, at the time of initial consent to the study, to a short telehealth video or telephone visit at 4-6 weeks postoperative. This research visit will administer the Patient Scar Assessment Scale (PSAS) questionnaire to assess for our primary outcome of patient scar satisfaction. Additionally, chart review will be performed at this time to assess for the presence of other secondary outcomes, such as wound complication.

The research team will perform chart review to abstract maternal demographics, delivery information, and maternal and neonatal outcomes from maternal and neonatal medical records. This information will be entered into REDCap, a web-based data collection system. Once the study is underway, an interim analysis using the previously described statistical methodology may be appropriate to ensure that there is not a disproportionate incidence of the primary composite outcome or other adverse outcome in the experimental group.

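### Mixed cesarean types enter one PSAS comparison with no covariate adjustment pre-specified; adjusting for two pre-operative factors would be a cheap, modest gain in precision.

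*Combined protocol and SAP*

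**What the plan says.** The Inclusion Criteria admit "All women scheduled for primary or repeat cesarean deliveries" and also "All women undergoing intrapartum or antepartum cesarean delivery". One trial therefore contains women with and without a previous cesarean, and both planned and unplanned operations.

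Study Design and Procedures describe a computer-generated 1:1 allocation made just before surgery: "Consenting women will be randomly assigned in a 1:1 ratio to each group by trained research personnel". No strata, blocks or minimisation are mentioned.

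Sample Size Calculation sets out a comparison of two PSAS means: 80% power, two-sided alpha 0.05, control mean 20 with SD 6, a 20% relative reduction, 20% loss to follow-up, and 94 women per arm. On variability it says "The standard deviation for both groups is assumed to be the same". It names no covariate. Procedures refers back to statistical methods described earlier, but no section describes any.

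On baseline data, Procedures says "The research team will perform chart review to abstract maternal demographics, delivery information, and maternal and neonatal outcomes". It does not itemise previous cesarean or the scheduled status of the operation.

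**The concern.** Cesarean type may be related to how a woman rates her scar four to six weeks later. PSAS asks about colour, stiffness, thickness and irregularity, and an earlier scar could plausibly affect these. If so, pooling the types without adjustment leaves explainable variation in the residual, and the interval on the primary outcome is wider than it need be. Both factors can be known before allocation, so adjusting for them is legitimate.

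The second issue is pre-specification. The trial is open label, the primary outcome is patient-reported, and no model is written down. Covariates could then be chosen after the outcome data are seen. Naming them now closes that option.

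**Working it through.** **Inputs from Sample Size Calculation.** SD 6 in each arm; target difference 20% of 20 = 4 points; alpha 0.05 two-sided; power 80%; loss 20%; 94 per arm.

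**Plan's own figure.** n per arm = 2 × (1.960 + 0.842)² × 6² / 4² = 35.3, so 36 (37 with the t distribution). After 20% loss, 37 / 0.80 = 46.25, so 47 per arm and 94 in total. The stated 94 per arm (188 total) is therefore not reproduced. That is a separate issue. The stated size is used below because it is what the trial plans to enrol.

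**Unadjusted precision.** Evaluable per arm: 94 × 0.80 = 75.2, taken as 75.
- SE = 6 × √(2/75) = 0.980.
- 95% half-width = 1.96 × 0.980 = 1.92 points.
- Power for 4 points (noncentral t) = 98.2%.

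**Adjusted precision.** Residual SD = 6 × √(1 − R²), where R² is the share of within-arm PSAS variance that the two factors explain. The documents give no R², so this is an assumed range.

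| Assumed R² | SE | 95% half-width | Power for 4 points |
|---|---|---|---|
| 0 | 0.980 | 1.92 | 98.2% |
| 0.02 | 0.970 | 1.90 | 98.4% |
| 0.05 | 0.955 | 1.87 | 98.6% |
| 0.10 | 0.930 | 1.82 | 99.0% |
| 0.20 | 0.876 | 1.72 | 99.5% |
| 0.30 | 0.820 | 1.61 | 99.8% |

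The table ignores the small cost of estimating two coefficients (residual degrees of freedom fall from 148 to 146), so at R² near zero there is no real gain.

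**Which R² is plausible?** Suppose half the women are repeat cases and repeat differs from primary by 3 points (both assumed). The explained variance is 0.5 × 0.5 × 3² = 2.25, and 2.25 / 36 = 6.25%. The half-width becomes 1.92 × √0.9375 = 1.86. For one such factor to explain 20% or 30%, the gap would have to be √(0.20 × 36 / 0.25) = 5.4 or √(0.30 × 36 / 0.25) = 6.6 points, more than the 4-point treatment target. The lower half of the table is the more realistic part.

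**Chance imbalance.** In the same scenario, the between-arm difference in the proportion of repeat cases has SD √(2 × 0.25 / 75) = 0.082. Its effect on the unadjusted estimate has SD 0.082 × 3 = 0.245 points, with 95% range ±0.48. The variance is 0.245² = 0.06, against SE² = 0.96, and 0.06 / 0.96 = 6.25%. This is the same 6.25% as above, already counted in the unadjusted standard error.

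**The case against.** The strongest reply is that the documents are silent rather than wrong. A sample-size calculation based on two means does not commit the trial to an unadjusted analysis, and a computer-generated algorithm could be stratified. This stands as a matter of reading: the root defect is the absent analysis section, and missing adjustment is one consequence. It does not remove the point, because the section has to be written and this is part of what it should say.

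A second reply is that the trial does not need the precision. With about 98% power for 4 points, adjustment adds at most 1.6 percentage points of power even at R² of 30%. This also stands. The gain would count for more if enrolment were cut to the roughly 94 in total that the plan's inputs support: at 37 evaluable per arm, R² of 10% raises power from 81% to 85%.

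A reader might infer more than the documents support:
- *That unstratified allocation biases the result.* It does not. Imbalance arises by chance, the unadjusted test keeps its type I error, and the variance is already in its standard error.
- *That wound complications gain in the same way.* The calculation applies to a linear model of a continuous score. Adjusting a logistic model for a binary outcome does not generally narrow the interval on the odds ratio, and the documents give no event rate.
- *That the covariates are already being collected.* The chart-review sentence only implies the two factors, and BMI appears nowhere.

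**Conclusion.** The point holds as a cheap improvement of modest size. The trial mixes cesarean types, specifies neither adjustment nor stratification, and describes only an unadjusted comparison of means. Adjusting for two factors known before randomisation would shorten the 95% interval by about 3%, 5% or 16% at assumed R² of 5%, 10% or 30% (half-width 1.92 to 1.87, 1.82 or 1.61). An assumed 3-point gap between primary and repeat cases, at 50% prevalence, corresponds to about 6%.

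These figures rest on the plan's SD of 6, on 75 evaluable women per arm, and on an R² that the documents do not supply. It would be wrong to conclude that the trial is underpowered or its primary comparison invalid for lack of adjustment. The reasons to act are a somewhat tighter estimate and a covariate set fixed before the outcome data are seen.

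**What to change.** - **Analysis text (Sample Size Calculation, or a new analysis section).** State that the primary analysis is a linear model of PSAS total on arm, adjusted for primary versus repeat cesarean and scheduled versus unscheduled (intrapartum or antepartum) cesarean, each as classified at randomisation. Report the unadjusted difference as a sensitivity analysis.
- **Data collection (Procedures).** List both factors explicitly among the chart-review items.
- **Stratification (optional).** Adjustment already gives most of the benefit. If the list is stratified by the same two factors, use concealed allocation and varying block sizes, because fixed blocks within strata in an open-label, single-site trial make upcoming assignments easier to guess.

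The cost is a sentence or two of text, two chart items and two of 148 residual degrees of freedom. No extra patients are needed. If enrolment has begun, the model can still be fixed, provided this is done before any interim look at outcomes and before the coded file goes to the analysts.

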#### Exclusion Criteria

- Vertical skin incision
- Cesarean hysterectomy
- Emergency or stat cesarean delivery excluding standard preoperative preparation measures (i.e. use of Chlorhexidine skin prep, vaginal prep, etc)
- Intrapartum stillbirth
- Planned postpartum follow up at another facility
- Contraindications to routine postpartum pain medications
- Allergy to skin glue/adhesive

#### Sample Size Calculation

The primary outcome of our study will be the Patient Scar Assessment Scale (PSAS), which has a range of potential scores from 6-60). The following assumptions were used for the parameters in our sample size calculation:

Power: 80%

Alpha level: 0.05 (two-sided)

Mean  $\pm$  SD for suture group:  $20 \pm 6$

Effect size: 20% reduction (relative to the control group)

Loss to follow up: 20%

Allocation Ratio: 1:1

The distributions of both groups are assumed to be normal.

The standard deviation for both groups is assumed to be the same.

The results were calculated in Stata/BE 17.0

With these assumptions, our total sample size is calculated to be 188 total patients, with 94 patients in each arm.

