## **Feasibility/Timeline**

There are approximately 30 cesarean deliveries per week at our institution. Assuming that 90% meet eligibility criteria, and assuming that 50% of patients agree to participate in the study, we will be able to recruit 1-2 patients per day. Thus, recruitment and enrollment will take approximately 4-6 months to reach the expected sample size of 188 patients.

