## **Anticipated Budget**

This goal of this proposal is to secure a charitable donation from Ethicon for 94 Dermabond Prineo units for use in this study as the experimental arm. The results of this study will aim to promote this product as an alternative to cesarean skin closure, and to increase its routine use at Columbia University Medical Center for our high volume obstetric practice. We cannot promote or endorse the use of this product until it has been shown to be a safe and non-inferior alternative to our current standard of skin closure with skin sutures at the time of cesarean delivery. Thus, we will need a donation of the Dermabond Prineo product in order to meet this goal.

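### The printed sample-size inputs give about 94 patients in total (47 per arm), not 188 (94 per arm), so the stated power and effect do not match the planned size

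*Combined protocol and SAP*

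**What the plan says.** The Sample Size Calculation section of the combined protocol and SAP takes the PSAS total score (possible range 6 to 60) as the primary outcome. It gives 80% power, two-sided alpha 0.05, a suture-arm mean of 20 with SD 6, a 20% reduction relative to control, 20% loss to follow-up and 1:1 allocation. Scores are taken as normal, and "The standard deviation for both groups is assumed to be the same". The calculation is attributed to Stata; the section names no test and shows no intermediate step. Its conclusion is: "With these assumptions, our total sample size is calculated to be 188 total patients, with 94 patients in each arm".

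The figure is used elsewhere. Feasibility/Timeline expects recruitment to take "approximately 4-6 months to reach the expected sample size of 188 patients". Anticipated Budget seeks "a charitable donation from Ethicon for 94 Dermabond Prineo units" for the experimental arm. So 94 per arm is the working target and not a slip confined to one sentence.

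**The concern.** The section says that its total follows from its listed assumptions, and those assumptions are complete enough to check. A 4-point difference against an SD of 6 is a standardised difference of 0.67. That does not call for 94 patients per arm at 80% power, even after allowing for 20% loss.

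This is the trial's only sample-size justification. If size, power and detectable effect contradict each other, an ethics or funding reviewer cannot tell which to believe. If the inputs are right, about 94 more women would be randomised, and 47 more devices requested, than the declared aim requires. If 188 is right, at least one printed input is not the one used, and the reader cannot tell which.

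**Working it through.** **Inputs (all from Sample Size Calculation).** Control mean 20; SD σ = 6 in both arms; relative reduction 20%; two-sided alpha 0.05; power 80%; 1:1 allocation; loss 20%.

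**Difference to detect.** δ = 0.20 × 20 = 4 points (20 against 16). Standardised difference d = 4/6 = 0.667.

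**Attempt to reproduce the stated 94 per arm.**

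Normal approximation, per arm:

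n = 2(z₀.₉₇₅ + z₀.₈₀)² σ²/δ² = 2 × (1.960 + 0.842)² × 36/16 = 2 × 7.849 × 2.25 = 35.3, so 36 evaluable.

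Two-sample t-test (noncentral t, d = 0.667): 36 per arm gives 79.7% power and 37 per arm gives 80.8%, so 37 evaluable.

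Allowance for loss, n/(1 − 0.20):

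- t-test: 37/0.8 = 46.25, so **47 per arm, 94 in total**
- normal approximation: 36/0.8 = 45 per arm, 90 in total

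The plan states 94 per arm and 188 in total. 188/94 = 2.0.

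**Variants that might explain the gap.** The first three rows keep 80% power and two-sided alpha 0.05. The next two raise the power. The last two change one printed input.

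| Variant | Per arm after 20% loss |
|---|---|
| Loss applied as × 1.2 instead of /0.8 | 44 to 45 |
| Mann–Whitney, relative efficiency 0.955 | 49 |
| Mann–Whitney, relative efficiency 0.864 | 54 |
| t-test, 90% power | 62 |
| t-test, 95% power | 75 |
| t-test, 15% reduction (3 points) | 80 |
| t-test, 12.5% reduction (2.5 points) | 115 |

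None gives 94.

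**What 188 delivers under the printed inputs.** 94 × 0.8 = 75.2, so about 75 evaluable per arm.

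- Power for 4 points at 75 per arm: 98.2%. With no loss (94 per arm): 99.5%.
- Difference detectable with 80% power at 75 per arm: 2.76 points; 2.76/20 = 13.8%.
- SD at which 75 per arm gives exactly 80% power for 4 points: 8.69, against the printed 6.

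**A possible source.** The stated per-arm number equals the correct total, 94. That is what would result if an inflated total were read as a per-arm size and doubled. This is an inference, since the plan does not show its working, and the mismatch does not depend on it.

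**The case against.** The strongest reply is that the error is in the safe direction. With 188 randomised the trial more than meets its declared 80% power for a 20% reduction, and its type I error is unaffected. All of that is correct. The point is a contradiction between stated figures and an unjustified number of participants, not a threat to the validity of the primary test.

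It can also be said that halving the trial would be unwise if the SD of 6 is too low. That has force. As an illustration only, with an SD of 8 the 4-point difference would have about 56% power at 37 evaluable per arm, against about 86% at 75. A smaller trial would also tell us less about wound complications, the first secondary question. These are reasons for the sponsor to settle the intended input before cutting the size. They do not justify 188 as written, because the section sizes the trial on the PSAS alone and gives no other reason.

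One might add that a larger trial can reach significance on a difference well below 20%. That deserves little weight, because it holds for any trial of ordinary size. The threshold for p < 0.05 is about 2.8 points at 37 per arm and about 1.9 points at 75. The doubling lowers the threshold but does not create the issue, and the plan does not call 20% a minimal important difference.

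Last, the section names no test, so 47 per arm rests on assuming a t-test. Other conventional choices at the stated power and alpha give roughly 44 to 54 per arm, still far from 94.

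**Conclusion.** The concern holds. Under the printed inputs the requirement is 37 evaluable and 47 randomised per arm, 94 in total (90 by the normal approximation). The plan states 188, a factor of two. At that size, with 20% lost, the trial has about 98% power for its declared 4-point effect, or 80% power for about 2.8 points (14%). Its stated 80% power for 20% does not describe it.

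This rests on a two-sample comparison of PSAS means with a common SD of 6 and on loss of exactly 20% in each arm. It should be corrected before the plan is relied on, because the headline sample size does not follow from its own stated basis. The trial is larger than its inputs require, not too small.

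**What to change.** First recover the Stata command or output, to establish which inputs were used. Then revise Sample Size Calculation in one of three ways, naming the test and showing the evaluable number before the allowance for loss:

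1. **Keep 188 and restate what it provides.** After 20% loss (about 75 per arm), this is about 98% power for a 4-point (20%) difference, or 80% power for about 2.8 points (14%) with SD 6. Give the reason for the larger size.
2. **Correct a misprinted input.** If another SD or effect was used, print it with its justification. An SD of just under 8.7 with a 4-point difference reproduces 94 per arm.
3. **Correct the total.** If the printed inputs are those intended and the sponsor is confident in the SD of 6, state 47 per arm and 94 in total. The device request in Anticipated Budget would fall from 94 to 47, and the recruitment period in Feasibility/Timeline would roughly halve.

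The third option should not be taken until the SD has been confirmed. Whichever is chosen, the three sections must agree. The cost is one corrected paragraph, plus matching figures in the two later sections if the total changes. No option needs more patients than are already planned.
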